**Table 4-1: Duration of Each Period**

Period	Duration
Screening Period	Prior to the date of first IMP administration (Relative Day -28 to -2)
Dosing Period 1	Defined as Relative Day -1, 1, 2, 3 and +1
Wash-out Period	Defined as Relative Day + 2 to + 6 (~ + 10)
Dosing Period 2	Defined as Relative Day -1, 1, 2, 3 and +1
Safety Follow-Up Period	Defined as Relative Day + 2 to + 7 (~ + 9)

#### 4.1.2 Definition of baseline values

Baseline will be the last available predose result for each Dosing Period. Each Dosing Period will therefore have its own Baseline, independent of the other Treatment Periods unless the data collection is not scheduled.

**Table 4-2: Definition of Baseline**

Measurement	Definition of Baseline
Vital Signs	Day 1, Pre-dose value in each period. If this value is unavailable, Day -1 check in value will be imputed in the period. If those values are unavailable, the latest available value before dosing will be imputed. For Dosing Period 1, the latest value in Screening Period and Dosing Period 1 before dosing can be used. For Dosing Period 2, the latest value in Wash-out Period and Dosing Period 2 before dosing can be used.
12-lead ECG	Day 1, Pre-dose value in each period. If this value is unavailable, the latest available value before dosing will be imputed. For Dosing Period 1, the latest value in Screening Period and Dosing Period 1 before dosing can be used. For Dosing Period 2, the latest value in Wash-out Period and Dosing Period 2 before dosing can be used.
Clinical laboratory tests (hematology, clinical chemistry, and urinalysis)	Day -1, check in value in each period. If this value is unavailable, the latest available value before dosing will be imputed. For Dosing Period 1, the latest value in Screening Period and Dosing Period 1 before dosing can be used. For Dosing Period 2, the latest value in Wash-out Period and Dosing Period 2 before dosing can be used. Baseline for Dosing Period 1 can be used for Dosing Period 2 if any other baseline value is unavailable.

#### **4.1.3 Mapping of assessments performed at Early Discontinuation Visit**

Safety assessments made at a withdrawal visit that correspond to a scheduled visit will be summarized at the scheduled visit to corresponding to the withdrawal visit if the assessment was scheduled to occur at that visit. Such assessments at the withdrawal visit will also be considered for safety follow up/ withdrawal visit.

#### **4.1.4 Treatment assignment and treatment groups**

Treatment assignment for the SS and PKS will be based on the actual treatment received in each Dosing Period.

Listings will be presented by treatment sequence, unless otherwise specified.

Summaries will be presented by treatment sequence or BRV formulation and overall, where applicable. The following order will be used in the Tables, Figures and Listings (TFLs): tablet, dry syrup and overall, where applicable.

For analysis conducted using the ES, an additional group for participants not randomized may be displayed, as applicable.

#### **4.1.5 Multicenter studies**

Not applicable since this study will be conducted at a single site.

#### **4.1.6 Center pooling strategy**

Not applicable since this study will be conducted at a single site.

### **4.2 Primary endpoint analyses**

Statistical analyses will be performed on the PKS.

The bioavailability of BRV dry syrup (1.25g of granules for oral suspension 4% w/w, corresponding to 50mg of BRV) (Test) will be compared with BRV 50mg tablet (Reference).

#### **4.2.1 Definition of endpoints**

The primary endpoints are defined as follows:

- Maximum plasma concentration at steady state,  $C_{max,ss}$
- Area under the curve during a dosing interval at steady state,  $AUC_{tau}$

#### **4.2.2 Main analytical approach**

The primary PK parameters  $C_{max,ss}$  and  $AUC_{tau}$  will be evaluated according to a linear mixed model, adapted to cross-over experimental designs. The model will include treatment (BRV formulation), period, and sequence as fixed effects. The participant (nested within the sequence)

will be included as a random effect. Since the participant is entered as a random effect in the linear mixed model, the data from the nonaffected Dosing Period (i.e., evaluable data) can still be used for the bioequivalence assessment even if the data from the other Dosing Period are excluded from the analysis. The dependent variables will be logarithmically (ln) transformed prior to statistical testing, following the usual recommendations.

This linear mixed model is represented as:

$$\log(Yijkl) = \mu + Si(j) + Qj + Fk + Pl + eijkl, \text{ where}$$

- $\log(Yijkl)$  is the log transformed PK parameter value of the  $i$ -th subject ( $i=1,2,3,..$ ) in the  $j$ -th sequence ( $j=1,2$ ); for the  $k$ -th treatment ( $k=1,2$ ) in the  $l$ -th period ( $l=1,2$ ),
- $\mu$  is the overall mean,
- $Si(j)$  is the random effect of the  $i$ -th subjects nested to the  $j$ -th sequence,
- $Qj$  is the fixed effect for the  $j$ -th sequence,
- $Fk$  is the fixed effect for the  $k$ -th treatment,
- $Pl$  is the fixed effect for the  $l$ -th period,
- $eijkl$  is the (residual) random error in observing  $\log(Yijkl)$ .

The MIXED procedure in SAS software will be used for this analysis.

For estimation based on a linear mixed model, covariance matrix applied to the within-subject error will be estimated by restricted maximum likelihood (REML). The Kenward-Roger approximation will be used to estimate the degree of freedom. Variance component structure will be used as covariance in this linear mixed model.

Adjusted geometric mean ratio (GMR) (Test/Reference) and the corresponding CIs will be calculated corresponding to the Lan-DeMets alpha spending function approximating a Pocock boundary ([Lan and DeMets, 1983](#)), while maintaining the overall 2-sided significance level of 0.1. Bioequivalence between the Test (dry syrup) and Reference (tablet) formulations will be concluded if the CIs for  $C_{max,ss}$  and  $AUC_{tau}$  are included in the range of 0.80 to 1.25. [IA-DMC, All]

SAS code for Lan-DeMets alpha spending function approximating a Pocock boundary

```
PROC SEQDESIGN bscale=pvalue;
  Pocock_type: design alpha=0.05 alt=upper stop=reject info=cum(percent_interim,1)
  nstages=2 method=ERRFUNCPOC ;
  RUN;
```

Note: **percent\_interim** is the number of participants for PKS at Interim analysis divided by 90.

For example, if an alpha is derived as 0.03817 for interim analysis, 2-sided (1 - 0.03817 times 2) times 100 % confidence interval for GMR will be derived to demonstrate the bioequivalence. Accordingly, 2-sided (1 -0.02704 times 2) times 100 % confidence interval for GMR will be derived to demonstrate the bioequivalence only if cohort 2 is conducted.

In the case that the CIs for  $C_{max,ss}$  and  $AUC_{tau}$  are not contained in the range of 0.80 to 1.25, bioequivalence can still be concluded if the following criteria are met:

- 1) The point estimate of the adjusted GMR (Test/Reference) for  $C_{max,ss}$  and  $AUC_{tau}$  are contained in the range of 0.90 to 1.11.
- 2) In vitro dissolution rates of Test (dry syrup) and Reference (tablet) formulations are available and are deemed similar according to [the Japanese bioequivalence guideline](#) (PSEHB/PED Notification No. 0319-1, 2020).

In parallel, the 1-sided (upper) 95% CI of the adjusted GMR (Test/Reference) for  $C_{max,ss}$  will be calculated to confirm if the upper boundary is less than 0.8700 for  $C_{max,ss}$ . [IA-DMC]

Inter-participant and intra-participant variability for each parameter will also be derived from these analyses as geoCVs. [IA-DMC, All]

Geometric least squares means and the corresponding 90% CI for each treatment (tablet or dry syrup) will be provided as well. [IA-DMC, All]

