6.3 Measures to minimize bias: randomization and blinding

This is an open-label study. Randomization will be involved only in the assignment of participants to the treatment sequence as per the cross-over design, treatment sequences A-B or B-A.

The study site will generate the randomization list for the treatment sequences (A-B or B-A) allocation. The randomization list will be reviewed by the Clinical Trial Statistician at UCB to ensure that the code meets the study requirements.

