In order to ensure a total of up to approximately 90 evaluable participants for the primary endpoints, assuming a rate of dropout and nonevaluable participants of approximately 5%, 64 participants for Cohort 1, 32 participants for Cohort 2, and up to 96 participants in total are estimated to be randomized in the study.

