#### **4.2.3 Supportive and sensitivity analyses**

Not applicable.

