### **4.7 Interim analyses**

The study may consist of 2 cohorts. A formal interim analysis is planned at the end of Cohort 1, once approximately 60 evaluable participants have completed the study. If bioequivalence or futility is not established in the interim analysis, the final analysis is planned at the end of Cohort 2, once all participants (approximately 90) have completed the study (See Section 9.8 of the protocol). The interim analysis, based on a group sequential design, will be an unblinded analysis performed by an internal statistical team independent from the study team and will focus on the analysis for primary PK parameters  $C_{max,ss}$  and  $AUC_{tau}$ . The results will be reviewed by an internal DMC, which is independent from the study team, and the following decisions will be made:

1. Early stopping of the study due to demonstrating bioequivalence at the end of Cohort 1:  
The study will be stopped early, after Cohort 1, if bioequivalence between the Test (dry syrup) and Reference (tablet) formulations is established for  $C_{max,ss}$  and  $AUC_{tau}$  (Section 9.3.1 of the protocol).
2. Early stopping of the study for futility at the end of Cohort 1:  
The study will be stopped early, after Cohort 1, in the event that bioequivalence is not established and the 1-sided (upper) 95% CI of the adjusted GMR (Test/Reference) is less than 0.8700 for  $C_{max,ss}$ . This corresponds to the GMR of this study being markedly lower than that of single-dose bioequivalence study (EP0110).
3. Continuing to Cohort 2:  
If bioequivalence or futility is not established, the study will continue to Cohort 2, and the remaining approximately 30 participants will be randomized.

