In the group sequential design for this study, an interim analysis will be performed for bioequivalence or futility after approximately 60 evaluable participants, which is at 90% power for bioequivalence based on the CIs of the adjusted GMR (Test/Reference) with the study assumptions. Should the assumption regarding variability and GMR not hold, with the study consequently not being stopped for demonstrating bioequivalence or futility at the interim analysis, this allows the opportunity to enroll a further approximately 30 participants and assess bioequivalence after approximately 90 evaluable participants. While maintaining the two 1-sided significance level of 0.05, this should be sufficient to state that the true GMR is in the range of 0.80 to 1.25. The two 1-sided significance levels currently used are 0.03817 for the interim analysis and 0.02704 for the final analysis according to the Lan-DeMets alpha spending function approximating a Pocock boundary, assuming 60 evaluable participants in Cohort 1 and 30 evaluable participants in Cohort 2 as the number of participants to be included in the analyses. A total of 90 evaluable participants will provide an overall power of >75% even if the GMR and intraparticipant CV% remain as observed in EP0110.

The probability of study stopping for demonstrating bioequivalence for Cohort 1 (power at Cohort 1), futility at Cohort 1, and proceeding to Cohort 2 are approximately 91%, approximately 1%, and approximately 8%, respectively. If the study continues to Cohort 2, the bioequivalence will be assessed after completing Cohort 2.

In order to ensure a total of up to approximately 90 evaluable participants for the primary endpoints, assuming a rate of dropout and non evaluable participants of approximately 5%, 64 participants for Cohort 1, 32 participants for Cohort 2, and up to 96 participants in total are estimated to be randomized in the study.

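### If Cohort 2 is run, the final model fits one period effect to two cohorts dosed at different times; the likely effect is small, and prespecifying cohort and period-within-cohort removes it for one degree of freedom

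*SAP*

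**What the plan says.** - **Model.** SAP 4.2.2: "The model will include treatment (BRV formulation), period, and sequence as fixed effects". Participant within sequence is random. Period has two levels for the whole trial. Protocol 9.3.1 gives the same model, and neither document gives a separate one for the final analysis.
- **Timing.** If the interim is inconclusive, SAP 4.7 says "the study will continue to Cohort 2, and the remaining approximately 30 participants will be randomized".
- **Pooling.** SAP section 5: "this allows the opportunity to enroll a further approximately 30 participants and assess bioequivalence after approximately 90 evaluable participants".
- **Allocation.** Protocol 6.3: "The study site will generate the randomization list for the treatment sequences (A-B or B-A) allocation". The same paragraph has the sponsor's trial statistician review the list. No block size or balance within cohort is given. Protocol 9.8 plans "64 participants for Cohort 1, 32 participants for Cohort 2, and up to 96 participants in total".
- **Sensitivity analyses.** SAP 4.2.3: "Not applicable".

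**The concern.** In a 2x2 cross-over the treatment effect is estimated from each participant's period difference. A cohort that runs higher or lower in both periods cancels out of that difference. A cohort whose change from period 1 to period 2 differs from the other cohort's does not cancel. With one common period effect, that discrepancy goes into the residual and widens the CI. If the two sequences also hold different shares of Cohort 2, part of it enters the treatment contrast.

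The final analysis is reached only after an inconclusive interim, where a narrow margin can decide the result. No alternative model is planned, so a cohort term added after the data were seen would be post hoc.

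**Working it through.** **Inputs from the documents (SAP section 5, Protocol 9.8).** 60 then 30 evaluable; one-sided levels 0.03817 and 0.02704; limits 0.80 to 1.25; futility if the one-sided 95% upper limit for Cmax,ss is below 0.87. Design values: GMR 0.89, SD 0.183. EP0110 values: GMR 0.87, CV 21.9%, so SD = sqrt(ln(1 + 0.219²)) = 0.216.

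**Assumed.** d, the log-scale difference between cohorts in the period effect (0, 0.05, 0.10, 0.20); the unbalanced split in step 3; complete two-period data.

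**1. The plan's own figures.** Pocock-type spending at 60/90 returns 0.03817 and 0.02704. A fixed design of 116 gives 90.1% power at EP0110 values (stated 90%). Simulating the two-stage design at design values gives 91.5% bioequivalence, 1.0% futility and 7.5% continuing (stated 91, 1 and 8%). At EP0110 values overall power is 77.9% (stated above 75%), and about 32% of trials continue.

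**2. Sequences balanced within cohort.** One third of each sequence is in Cohort 2, so d adds d² x (2/3)(1/3)/2 = d²/9 to the residual variance, times 90/88 for degrees of freedom. The CI widens by the factor sqrt(1 + (d²/9)(90/88)/SD²).

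- Example, d = 0.20, design SD: added variance 0.00444 x 90/88 = 0.00455; 0.00455/0.0335 = 0.136; sqrt(1.136) = 1.066.

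| d | CI wider, EP0110 SD | CI wider, design SD | Power, EP0110 values | Power, design values |
|---|---|---|---|---|
| 0 | 0 | 0 | 77.9% | 97.5% |
| 0.05 | 0.3% | 0.4% | 77.8% | 97.5% |
| 0.10 | 1.2% | 1.7% | 77.4% | 97.4% |
| 0.20 | 4.7% | 6.6% | 76.1% | 97.1% |

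Power is for the whole trial by the CI route. With the cohort terms it is about 77.8 to 77.9% and 97.5% at every d. Simulated percentages are good to about 0.1 point. The GMR does not move.

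**3. Sequences not balanced within cohort (illustration: 28/32 then 17/13, 45/45 overall).** The log GMR shifts by 0.5 x d x (difference between sequences in Cohort 2 share):

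- d = 0.10: 0.5 x 0.10 x (17/45 - 13/45) = 0.0044
- d = 0.20: 0.5 x 0.20 x (4/45) = 0.0089, so a GMR of 0.892 would read as 0.900

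| Size of d | Type I error at GMR 0.80, SD 0.183 | Same, EP0110 SD | Power, EP0110 values |
|---|---|---|---|
| 0.10 | 4.4% or 5.3% | 4.5% or 5.5% | 74.9% or 80.1% |
| 0.20 | 4.0% or 5.6% | 4.1% or 5.9% | 71.2% or 81.4% |
| any, with the terms | about 4.8% | about 5.0% | about 77.6% |

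The two values in a cell are the two directions of d. Averaged over random allocation, type I error without the terms is at most 4.9% at SD 0.183, and 5.1% at the EP0110 SD with d = 0.20.

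**4. AUCtau.** With a CV of 2.7%, d = 0.10 widens the CI by 59%, but the half-width is still only 0.0125 on the log scale and power stays at 100%. Only Cmax,ss matters here.

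**The case against.** The strongest reply is that nothing in the documents shows harm. d is assumed. The study has one site, and the confinement, fasting, sampling and wash-out rules are the same throughout, so a 10 to 22% difference between cohorts in the period effect (d = 0.10 to 0.20) is not an obvious expectation. At d = 0.05 with balance, the power lost is about 0.1 point or less. At design values only about 8% of trials reach the final analysis. This stands, and it is why the point is minor.

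A reader might go further and infer that the plan inflates type I error or biases the GMR. The documents do not support that. Protocol 6.3 is silent on blocking, but silence is not evidence of imbalance. The sponsor's statistician reviews the list, and 64 and 32 can each be split equally. A probability for an uneven split would need an allocation method that the documents do not state. The type I error figures above 5% need the assumed d, the assumed split and the adverse direction together.

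Three other readings also fail:

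- **Single-period participants let a cohort level shift leak in.** SAP 4.2.2 says "the data from the nonaffected Dosing Period (i.e., evaluable data) can still be used for the bioequivalence assessment", but SAP 3.4 and Protocol 9.3.1 also tie inclusion to reliable primary parameters for both formulations, so the documents pull both ways. Even with four Cohort 2 participants assumed to have only the tablet period, the log GMR moves by 0.001 to 0.002.
- **The point-estimate route is put at risk.** SAP 4.2.2 makes "The point estimate of the adjusted GMR (Test/Reference) for" the two primary parameters a criterion with limits 0.90 to 1.11. For Cmax,ss, a final estimate of 0.90 already has a lower limit of about 0.90 x exp(-0.0531) = 0.853 (design SD) or 0.90 x exp(-0.0628) = 0.845 (EP0110 SD). The CI route would already have passed.
- **The factor should be dosing group, at the interim too.** The documents describe cohorts only. The interim uses Cohort 1 alone and is not affected.

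**Conclusion.** The point holds as a small, inexpensive improvement to the final analysis. The model contains no term for a cohort difference in the period effect, and two cohorts separated by an interim analysis could have one. With balance within cohort, the only cost is power: about 0.5 point at d = 0.10 and under 2 points at d = 0.20 at EP0110 values, and 0.1 and 0.4 point at design values. A GMR shift of 0.0044 to 0.0089 on the log scale, with type I error of about 4.0 to 5.9%, arises only if the realised split is as uneven as in the illustration. Over allocation, type I error stays at about 5%.

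All of this rests on assumed values of d and, for the shift, an assumed imbalance. The absence of a statement on balance within cohort is missing detail, not a contradiction.

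**What to change.** Before the interim data are seen, add one line to SAP 4.2.2: if Cohort 2 is run, the final-analysis model also includes cohort and period-within-cohort as fixed effects. Leave the interim model unchanged.

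Cost with complete data: residual degrees of freedom go from 88 to 87. If sequences are balanced within cohort and d = 0, no power is lost. In the 28/32 then 17/13 illustration at d = 0, the effective size n1 x n2/(n1 + n2) falls from 45 x 45/90 = 22.5 to 28 x 32/60 + 17 x 13/30 = 22.3. The CI is then about 0.5% wider (sqrt(22.5/22.3) = 1.0045, plus the lost degree of freedom), and power drops by about 0.1 point at design values and 0.3 point at EP0110 values. No extra participants or data are needed.

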9.5 Handling of protocol deviations

All protocol deviations will be reviewed on an ongoing basis as part of the data cleaning and evaluation process. After all data have been verified/entered into the database, and prior to database lock, a Data Evaluation Meeting will be performed for each cohort. The purpose of this review meeting will be to examine all protocol deviations, define the PKS (Section 9.1), and to verify the quality of the data. If PK parameters are needed to define the PKS, it will be performed based on the analysis data set of the pharmacokinetic parameters. The data evaluation will also help in guiding decisions on how to manage data issues on a case-by-case basis (eg, missing values, dropouts, and protocol deviations).

Accepted deviations from theoretical time points will be described in the appropriate documents and included in the electronic Trial Master File. After the data review, resolution of all issues, and documentation of all decisions, the database will be locked.

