In the event that EP0231 will have results similar to those observed in EP0110 without any improvement by the multiple-dose study design, 116 participants will be needed to provide a power of 90% with a fixed design (no interim analysis). However, because this study is conducted as a multiple-dose study, it is expected that the PK profile variability will be smaller. It is assumed that both the GMR and intraparticipant SD will show improvement (higher GMR and smaller intraparticipant SD) compared with the single-dose study (EP0110), closer to those shown in the multiple-dose PK simulation results. The study assumptions for GMR and intraparticipant CV% (for C_{max}) are based on the approximate middle values of those seen in EP0110 and the multiple-dose PK simulations based on the EP0110 study data, assuming a GMR of 0.89 and intraparticipant SD of 0.183 (corresponding to a CV% of 18.5%).

In the group sequential design for this study, an interim analysis will be performed for bioequivalence or futility after approximately 60 evaluable participants, which is at 90% power for bioequivalence based on the CIs of the adjusted GMR (Test/Reference) with the study assumptions. Should the assumption regarding variability and GMR not hold, with the study consequently not being stopped for demonstrating bioequivalence or futility at the interim analysis, this allows the opportunity to enroll a further approximately 30 participants and assess bioequivalence after approximately 90 evaluable participants. While maintaining the two 1-sided significance level of 0.05, this should be sufficient to state that the true GMR is in the range of 0.80 to 1.25. The two 1-sided significance levels currently used are 0.03817 for the interim analysis and 0.02704 for the final analysis according to the Lan-DeMets alpha spending function approximating a Pocock boundary, assuming 60 evaluable participants in Cohort 1 and 30 evaluable participants in Cohort 2 as the number of participants to be included in the analyses. A total of 90 evaluable participants will provide an overall power of >75% even if the GMR and intraparticipant CV% remain as observed in EP0110.

The probability of study stopping for demonstrating bioequivalence for Cohort 1 (power at Cohort 1), futility at Cohort 1, and proceeding to Cohort 2 are approximately 91%, approximately 1%, and approximately 8%, respectively. If the study continues to Cohort 2, the bioequivalence will be assessed after completing Cohort 2.

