### 2.1 Multiplicity adjustment

Since the analyses of primary endpoints are planned at the interim analysis and the final analysis, Lan-DeMets alpha spending function approximating a Pocock boundary will be applied in order to control the overall Type I error rate.

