### 3.4 Pharmacokinetic Set

The Pharmacokinetic Set (PKS) consists of all study participants who are randomized, receive at least 1 dose of active IMP and have at least 1 quantifiable post-Baseline PK measurement.

All PKS participants who have a sufficient number of bioanalytical assessments to calculate reliable estimates for the primary PK parameters for both BRV formulations will be included in the statistical analysis.

If a participant's predose concentration on Day 1 is greater than 5% of the  $C_{max,ss}$  value on Day 3 in a Dosing Period, the participant's data from that Dosing Period will be excluded from the statistical analysis. If a participant's predose concentration on Day 1 is greater than 5% of the  $C_{max,ss}$  value on Day 3 for both Dosing Periods, the participant will be excluded from the statistical analysis.

If vomiting occurs at or before 2 times the median  $t_{max,ss}$  for the tablet and the dry syrup within a Dosing Period, the participant's data from that period will be excluded from the statistical analysis. If vomiting occurs at or before 2 times the median  $t_{max,ss}$  within a Dosing Period, for both Dosing Periods, the participant will be excluded from the statistical analysis.

If (1) a PK sample is missing and the  $C_{max,ss}$  is the sample immediately preceding or following the missing sample or (2) 2 or more samples are missing, then the participant's data from that period will be excluded from the statistical analysis.

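### SAP 4.2.2 fixes final information at 90 and has no step to re-solve the final significance level for the number actually analysed, so the overall level drifts slightly whenever that number is not 90

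*SAP*

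**What the plan says.** SAP 2.1 says that a Lan-DeMets spending function of Pocock type "will be applied in order to control the overall Type I error rate". SAP 4.2.2 implements it with a single two-stage call, "design alpha=0.05 alt=upper stop=reject info=cum(percent_interim,1"), in which percent_interim "is the number of participants for PKS at Interim analysis divided by 90". Final information is therefore 90 whatever happens later.

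SAP 4.2.2 then illustrates the use of the output. An interim alpha of 0.03817 gives the interim interval, and 0.02704 from the same run gives the level at which the "confidence interval for GMR will be derived to demonstrate the bioequivalence only if cohort 2 is conducted". Protocol 9.8 and SAP 5 state the same two levels, "assuming 60 evaluable participants in Cohort 1 and 30 evaluable participants in Cohort 2 as the number of participants to be included in the analyses".

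The sample sizes are approximate. Protocol 9.8 plans randomization "assuming a rate of dropout and nonevaluable participants of approximately 5%, 64 participants for Cohort 1, 32 participants for Cohort 2", up to 96 in total.

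The count that feeds the fraction is the Pharmacokinetic Set. Under SAP 3.4 a randomized participant enters it if they "receive at least 1 dose of active IMP and have at least 1 quantifiable post-Baseline PK measurement". Separate rules in that section then remove participants or periods from the statistical analysis. Protocol 9.5 has a data evaluation meeting for each cohort to "examine all protocol deviations, define the PKS (Section 9.1), and to verify the quality of the data".

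**The concern.** A spending-function design holds its level because the last boundary is solved from the alpha already spent and the correlation between the two looks. That correlation is the square root of the ratio of interim to final information. SAP 4.2.2 adapts to the interim count but assumes the final count is exactly 90. The correlation used to set the final level can differ from the real one in two ways:

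- The number analysed after Cohort 2 is not 90. The protocol's own loss rate gives 64 × 0.95 = 60.8 and 96 × 0.95 = 91.2, so about 61 then 91.
- The interim Pharmacokinetic Set count differs from the number contributing to the primary model. Whether this can happen depends on what the data evaluation meeting does. If the two counts are always equal, only the first route remains.

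The final level sets the width of the confidence interval that decides bioequivalence after Cohort 2. If more than 90 are analysed, the promised overall level is slightly exceeded. If fewer are analysed, the interval is wider than it needs to be.

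**Working it through.** **Inputs.** Overall one-sided alpha 0.05, rejection boundary only, Pocock-type error spending, two stages (SAP 4.2.2). Planned counts 60 then 90; randomized 64 then 96 with about 5% loss (Protocol 9.8). Futility if the upper one-sided 95% limit for the Cmax,ss ratio is below 0.87 (Protocol 9.7, SAP 4.7). Design SD 0.183; EP0110 CV 21.9%; simulated multiple-dose CV 15.3% (Protocol 9.8).

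**Formulas.**
- Interim level: a1 = 0.05 × ln(1 + (e − 1)t), with t = interim Pharmacokinetic Set count / 90.
- Final level under the SAP: a2 such that a1 + P(Z1 < c1, Z2 > c2) = 0.05, with correlation √t, where c1 and c2 are the upper normal quantiles of a1 and a2.
- Realised error: the same a1 and a2, with the true correlation √(n1/n_final).
- Re-solved final level: a1 held, a2 solved so that the total is 0.05 at the true correlation.

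**The plan's own figures.** At t = 60/90, a1 = 0.03817 and a2 = 0.02704, with total error 0.0500. Both stated levels reproduce.

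**Realised one-sided error under the SAP rule, no futility credit.**

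| Interim count used | Analysed: interim, final | a1 / a2 from SAP code | Realised error | Re-solved a2 |
|---|---|---|---|---|
| 60 | 60, 90 | 0.03817 / 0.02704 | 0.0500 | 0.02704 |
| 61 | 61, 91 | 0.03861 / 0.02692 | 0.0502 | 0.02662 |
| 60 | 60, 92 | 0.03817 / 0.02704 | 0.0504 | 0.02648 |
| 64 | 64, 96 | 0.03992 / 0.02662 | 0.0511 | 0.02475 |
| 64 | 60, 90 | 0.03992 / 0.02662 | 0.0511 | 0.02475 |
| 60 | 60, 85 | 0.03817 / 0.02704 | 0.0490 | 0.02865 |
| 60 | 60, 80 | 0.03817 / 0.02704 | 0.0478 | 0.03069 |

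The row 64, 96 assumes no losses at all. The row with 64 counted and 60 then 90 analysed assumes that all of Cohort 1 enters the Pharmacokinetic Set.

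**With the futility stop always obeyed.** At a true ratio of 0.80, the study stops when Z1 < ln(0.87/0.80)/SE1 − 1.645, with SE1 = SD × √(2/n1). A CV of 21.9% is an SD of √ln(1 + 0.219²) = 0.2164, and a CV of 15.3% is 0.1521.

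| Case | SD 0.183 | CV 21.9% | CV 15.3% |
|---|---|---|---|
| 61 then 91 | 0.0487 | 0.0499 | 0.0442 |
| 64 then 96 | 0.0493 | 0.0507 | 0.0442 |
| 64 counted, 60 then 90 analysed | 0.0498 | 0.0508 | 0.0455 |

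**Effect on the decision.** The half-width on the log scale is t × SD × √(2/n), with t on n − 2 degrees of freedom. The lowest point estimate that clears 0.80 is 0.80 × exp(half-width). Moving to the re-solved level has these effects:
- 61 then 91: interval 0.3% wider.
- 64 then 96, or 64 counted with 60 then 90 analysed: 1.7% wider. At n = 90 and SD 0.183 the lowest passing ratio moves from 0.8439 to 0.8447.
- 60 then 80: 3% narrower. The lowest passing ratio moves from 0.8466 to 0.8452.

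**The case against.** The strongest reply is that the effect is too small to matter. At 61 then 91 the excess is 0.0002, about the size of the gap between normal theory and the t-based intervals that the mixed model will give. Simulation with t-based intervals puts 60 then 90 itself at about 0.0501 to 0.0502. If the futility stop is obeyed, the error falls below 0.05 at the design SD. To exceed 0.05 in the 64 then 96 case then takes both no losses and no improvement on the EP0110 variability. Cohort 2 is itself unlikely under the design assumptions. All of this stands and sets the severity. It does not remove the point: the SEQDESIGN call has no futility boundary, so the plan claims no such credit, and at 64 then 96 the t-based error is about 0.0513 before re-solving and 0.0501 after.

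A second reply is that the SAP gives the levels as an example and the protocol ties them to 60 and 30, so an update might be meant. No figure is miscalculated, and nothing forbids an update. But the SAP does state a rule for deriving both levels, and that rule contains no update. A level chosen after interim results are known is what pre-specification should prevent.

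A third reply is that the Pharmacokinetic Set route is conjectural, because the data evaluation meeting may make the set equal to the analysed number. That is fair, and the route is treated as conditional here. It is also true that counting participants only approximates information, because SAP 4.2.2 lets participants with one usable period into the model.

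**Conclusion.** The concern holds and is minor. The stated levels are right for 60 then 90. The rule in SAP 4.2.2 does not maintain the overall level for other final numbers. On the SAP's own accounting the one-sided error is 0.0502 at the numbers implied by the protocol's loss rate. It reaches 0.0511 at the upper end examined, and falls to 0.0478 if only 80 are analysed. With futility always obeyed, the over-run cases tabulated exceed 0.05 only at the EP0110 variability.

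These figures rest on normal theory, on information proportional to the number of participants, and on the confidence-interval criterion alone. The alternative route through point estimates and dissolution is not included.

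**What to change.** Add to SAP 4.2.2 that at the final analysis the alpha spent at the interim is held. The stage-2 level is then re-solved from the actual interim-to-final information ratio of participants contributing to the primary model (for example with PROC SEQTEST), and that level is used for the final confidence interval. State how participants with one usable period are counted, and that no credit is taken for the futility stop, as in the present code.

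The definition of percent_interim need not change for error control. With a true ratio of 60/90, an interim alpha set from a count of 56, 60 or 64 gives re-solved final levels of 0.0292, 0.0270 and 0.0247, each with a total of 0.0500.

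The cost is a few lines of text and code. The final interval becomes up to about 2% wider on the log scale if more than planned are analysed, and about 3% narrower at 60 then 80. It is unchanged at 60 then 90.
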